
Power analysis. We used the simulated-based power calculation method by Zhang et al.¹³³ for interrupted time series analysis to conduct power analysis for Aim 1. With the expected ~49,000 ICU-days of ~15,000 patients in 68 ICUs, we generated 1,000 simulations with various patient subgroup distributions and proportion of ICU days with bundle performance during the pre-implementation and implementation periods. Our preliminary analyses of the pre-implementation period data suggest that the probability of bundle performance ranged from 0.05 (for complete bundle performance) to 0.60 (for performance of element A) at the end of the pre-implementation period and a monthly increase in the probability ranged from zero (for element E) to 0.05 (for element D). To be conservative in power calculation, we used a probability of 0.05 for the level and a 0.05 monthly increase in the probability for the slope in the pre-implementation period. Our power analysis suggested that our data will have 80% power to detect an odds ratio (OR) of 1.25 (corresponding to an increase of 0.02 in the probability of receiving bundle performance) and 80% power to detect a slope change, with an OR of 1.52 corresponding to pre- vs. post-difference of 0.03 in the monthly increase of the probability of receiving bundle care. Based on our preliminary data, we reasonably assumed an autocorrelation of 0.5 under the first order auto-regressive covariance structure, a within-patient correlation of 0.5, and a within-hospital correlation of 0.6 in our simulation-based power calculation. Under the same assumptions, we also conducted power analyses on the effects of patient characteristics on the level and slope changes. For patient characteristics with 20:80 distribution, our sample size will have 80% power to detect an OR of 1.73 for the effect of patient characteristics on level change and 80% power to detect an OR of 2.65 for the effect of patient characteristic on slope change. The above power calculation is the most conservative scenario. The study power will be greater than 80% for other cases (e.g., pre-probability of 0.5, patient characteristics with 50:50 distribution). Regardless of study power, we will report point estimates, 95% confidence intervals, and use clinical significance to guide results interpretation. All above calculations were based on multilevel segmented logistic regression with a 0.05 two-sided significance level and adjusted for data dependencies described above.

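### At its stated baseline, Aim 1's detectable level change pairs two different effects (OR 1.25 is +0.012, not +0.02), and the 80% power claimed for it cannot be verified from the stated inputs

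*Combined protocol and SAP*

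**What the plan says.** The Aim 1 power analysis is simulation-based, with about 49,000 ICU-days, about 15,000 patients and 68 ICUs. It reports that the pre-period probability "ranged from 0.05 (for complete bundle performance) to 0.60 (for performance of element A) at the end of the pre-implementation period". It then states that "we used a probability of 0.05 for the level and a 0.05 monthly increase in the probability for the slope in the pre-implementation period". The dependence inputs are a first-order autocorrelation of 0.5, "a within-patient correlation of 0.5, and a within-hospital correlation of 0.6".

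From these it reports "80% power to detect an odds ratio (OR) of 1.25 (corresponding to an increase of 0.02 in the probability of receiving bundle performance"). Under shared assumptions it also reports "80% power to detect an OR of 1.73 for the effect of patient characteristics on level change", for a 20:80 split. It adds that "The above power calculation is the most conservative scenario" and that "The study power will be greater than 80% for other cases". Aim 2, Sample Size/Power Analysis, reuses the approach and the same most conservative scenario for an OR of 1.80 for the effect of an implementation strategy on level change.

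Three other places matter. Aim 1, Data analysis, codes the pre-period as Months -5 to 0 and the implementation period as Months 1 to 14. Aim 1, Procedures and Data Sources, gives 5 patients per site per month before and 15 after. Preliminary Data reports baseline complete-bundle performance below 4% with a relatively flat pre-trend.

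**The concern.** An odds ratio and a probability difference describe one effect only at a particular baseline. At the baseline the plan names, the two halves of its headline figure disagree, and power differs a good deal between them. The level and slope also come from different outcomes: 0.05 is the complete-bundle value and 0.05 per month is the element D trend. No one outcome is said to follow that path.

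What is at stake is how null results are read. A null level change for complete bundle performance, or a null patient-characteristic effect on it, could be taken as adequately powered on the strength of these sentences. The harm is limited to interpretation: the data already exist, and the plan commits to point estimates and confidence intervals whatever the power.

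**Working it through.** **1. The printed pair.** Odds at 0.05 are 0.05/0.95 = 0.05263.
- OR 1.25: odds 0.06579, probability 0.0617, difference +0.012.
- +0.02: (0.07/0.93)/(0.05/0.95) = 1.43.
- OR 1.25 rounds to +0.02 only for baselines of about 0.065 to 0.116. At 0.10 it is +0.022.

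**2. The path.** The 0.05 is an end-of-pre-period value, which is Month 0 in the plan's coding. On the probability scale, p = 0.05 + 0.05 x Month. That is 0 at Month -1 and 0.05 - 0.25 = -0.20 at Month -5. Placing 0.05 at Month -5 instead gives 0.05 + 0.05 x 19 = 1.00 at Month 14. The scale is not stated.

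**3. Power at OR 1.25.** Inputs from the plan: 68 ICUs; 20 months; 5 then 15 patients per ICU-month; the terms intercept, Month, Imp and Month x Imp; two-sided 0.05. That is 68 x (6 x 5 + 14 x 15) = 16,320 patients against 15,226 reported; scaling down lowers power by 1-3 points. Days per patient are taken as 3.2 (the plan says 3.3).

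Let h be the hospital correlation and r the total within-patient correlation. On standardised residuals, the mean for an ICU-month with n patients and m days each has variance [(1 - r)/m + (r - h)]/n, plus h shared across that ICU's months. Weighting each month's design row by the square root of p(1 - p) and summing the information over 68 ICUs gives the SE of the level change. Power is Phi(ln 1.25/SE - 1.96), with ln 1.25 = 0.223. Power of 80% needs SE = 0.223/2.80 = 0.080.

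Where two values appear, they come from evaluating p(1 - p) with and without the level change.

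| h / r | flat 5% | flat 4% | flat 10% | logit rise, 0.05 at Month 0, 0.10 at Month 1 |
|---|---|---|---|---|
| 0 / 0.5 | 29% | 24-25% | 48-49% | 22% |
| 0.3 / 0.5 | 46-47% | 39-40% | 73-74% | 35% |
| 0.6 / 0.8 | 54-60% | 46-51% | 82-86% | 44% |
| 0.6 / 0.6 | 80-89% | 70-82% | 98-99% | 75% |

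Worked cell: flat 5%, 0/0.5, SE 0.158; 0.223/0.158 - 1.96 = -0.55; power 29%. For 0.6/0.6 with the level change included, SE is 0.080 and power 80%.

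The row 0.6/0.8 reads 0.5 as conditional on hospital (0.6 + 0.4 x 0.5). The 0.3 is Aim 2's between-ICU value. In 0.6/0.6 patients add nothing beyond the hospital. If both stated values were total, 0.5 could not lie below 0.6, because days on one patient share that patient's hospital.

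A binary-data simulation of flat 5% (700 runs) gave 44% at 0.3/0.5 and 54% at 0.6/0.8. The table omits the autocorrelation. In a separate calculation (54% at flat 5% with patient 0.5 and hospital 0.6), applying it to monthly errors gave 51%; applying it to the hospital-by-month effect itself gave 8%.

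**4. The other half of the pair.** At flat 5%, power at OR 1.43 is 61-94% over the first three rows, against 29-60% at 1.25.

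**5. Most conservative scenario.** Within each row, flat 4% gives less power than flat 5%. The logit rise is about as demanding as flat 4%. A baseline below 4% also permits flat 2% (an illustration, not a plan value), which gives 15-29% over the first three rows and, row by row, less than the logit rise. The plan's own example of a pre-probability of 0.5 does hold (89% or more).

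**The case against.** The strongest reply is that the figure came from a simulation whose path and correlation structure are not fully printed, so a failure to match it may reflect the reconstruction. This largely stands. Two readings recover about 80%: flat 5% with 0.6/0.6, and flat 10% with 0.6/0.8. The second also fits the printed +0.02, and 0.10 is what 0.05 plus one month's rise gives at Month 1. Neither is what the text states. The first leaves the within-patient 0.5 with no role, and the second holds constant a baseline that the plan describes as 0.05 and rising. But they rule out the stronger conclusion, which a reader might draw from the table, that 80% power is definitely not delivered.

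A reader might also infer that 1.73 and 1.80 were scaled from 1.25. For a 20:80 split, 1/sqrt(0.2 x 0.8) = 2.5 and 1.25^2.5 = 1.75; the implied factors are ln 1.73/ln 1.25 = 2.46 and ln 1.80/ln 1.25 = 2.63. The closeness is suggestive, but the plan describes separate power analyses under common assumptions, so only shared inputs are documented.

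Third, it is tempting to apply the same conversion to the slope figure, "with an OR of 1.52 corresponding to pre- vs. post-difference of 0.03 in the monthly increase". In the plan's model that OR is a ratio of monthly odds ratios, not a comparison of 0.05 with 0.08. A first-month rise from 0.05 to 0.13 instead of 0.10, for example, gives (0.13/0.87)/(0.10/0.90) = 1.34. The answer depends on the unstated path, and no error is claimed there.

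Finally, the below-4% figure describes the whole baseline period and 0.05 its end, so the two need not conflict. With a relatively flat trend they are hard to bring far apart, but this is a reason to add a lower case, not proof that 0.05 is wrong.

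**Conclusion.** The headline level-change figure is internally inconsistent: at the stated 0.05, OR 1.25 is +0.012 and +0.02 is OR 1.43. This is plain arithmetic and needs no modelling assumption. The scenario is incoherent as written if the path is on the probability scale and 0.05 sits at Month 0, which is where the text places it.

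The 80% is unverifiable. It fails most readings (about 29-60% at flat 5%) and is met under two that the plan does not state. Those percentages rest on a constant hospital effect, no random slopes and an assumed placement of the correlations, so they show sensitivity and are not replacement values. The 1.73 and 1.80 figures inherit the input problem through shared assumptions. The claim to be the most conservative case is not established for complete bundle performance. The consequence is confined to how null findings are interpreted.

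**What to change.** State the month at which 0.05 applies, the scale of the baseline path, where the autocorrelation of 0.5 acts, and whether 0.5 and 0.6 are total or conditional correlations. Rerun the simulation with 5 and 15 patients per site-month, and include a flat complete-bundle case at 4% or lower. Restate the detectable level OR with its probability difference computed at the stated baseline. Carry the corrected inputs into the Aim 1 patient-characteristic figures (1.73 and 2.65) and the Aim 2 strategy figures (1.80 and 2.96). Limit the statements that the scenario is the most conservative and that power exceeds 80% elsewhere to what the rerun shows.

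The cost is rerun time, and some detectable odds ratios may become less favourable.

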Our preliminary data also show that collaborative participation resulted in significant but highly variable ABCDEF bundle adoption. Our next goal was to determine if collaborative participation led to increased bundle adoption. We were interested in exploring if some sites were "better" ABCDEF bundle adopters than others. The presence of a substantial amount of variability in our data would present us the opportunity to learn both from high- and low-bundle-performing sites. We calculated monthly rates of complete bundle performance, proportional bundle performance, and element-specific performance for the 17,258 patients across 49,109 full ICU days. We used segmented regression analysis for interrupted time series data to model the linear trend of bundle performance rates as a function of time for each segment (1-6 months pre-Collaborative involvement and 7-20 months during the Collaborative).

Complete bundle performance levels were low in the baseline (pre-Collaborative) period (i.e., < 4%). Complete bundle performance increased 2.0% (SE = 0.9%, $P = 0.057$) immediately after joining the Collaborative, and each month was associated with 0.6% greater increase (SE = 0.2%, $P = 0.038$) in complete bundle performance rates, compared to a relatively flat trend in the pre-Collaborative period. Proportional bundle performance rates also significantly increased by 3.8% (SE = 1.6%, $P = 0.026$) immediately after joining the Collaborative, then increased monthly at the same speed as the trend in the pre-Collaborative period (2%, SE = 0.4%, $P = 0.57$).

Bundle performance was highly variable among ICUs and across individual bundle elements; interquartile ranges of > 20% existed for all performance measures. (**Figure 1**) Elements A, C, D, and F were performed on average $\geq 70\%$ of the time at the end of the Collaborative:

Figure 1. Variation among ICUs in Unadjusted ABCDEF Bundle Performance Rates

adoption of elements B1, B2, and E (SATs, SBTs, and early mobility) proved far more challenging. For example, at the end of the Collaborative, an average $\leq 40\%$ of patients participated in early mobility and less than half of patients requiring MV received a daily SBT. Although overall performance was relatively poor, there were indeed some very good bundle performers.

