Sample Size/Power Analysis. The reliability of ICU-specific performance rates depends on sample size in each hospital (ICU days after adjusting for within-patient clustering). Using the Spearman-Brown prophecy formula,^{138,139} a minimal sample size of 10 is needed to generate reliable ICU-specific estimates (reliability ≥ 0.8), assuming an intraclass correlation of 0.3 for between-ICU variation based on our preliminary analysis. Given the large number of observations in our data ($\sim 49,000$ ICU patient-days nested in $\sim 15,000$ patients in 68 ICUs), there will be sufficient sample size to generate an ICU-specific performance estimate with ≥ 0.8 reliability, even conservatively assuming a large within-patient correlation of 0.8. We conducted power analysis for the effects of organization-level characteristics using the same simulation-based approach described for Aim 1 power analysis. Under the most conservative scenario (see power analysis of Aim 1), our sample size will have sufficient power ($\geq 80\%$) to detect an OR of 1.80 for the effect of an implementation strategy (used vs. not used by the site) on level change and an OR of 2.96 for the effect of an implementation strategy in slope change, assuming 20:80 distribution of the implementation strategy (used vs. not used by the site).

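### The 80%-power figures for level change and slope change (OR 1.25/1.52, 1.73/2.65, 1.80/2.96) do not fit together, so at least one figure in each pair is wrong or rests on unstated inputs

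*Combined protocol and SAP*

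**What the plan says.** The Aim 1 Power analysis reports a simulation based on "multilevel segmented logistic regression with a 0.05 two-sided significance level". Its claim for the overall slope change is "80% power to detect a slope change, with an OR of 1.52 corresponding to pre- vs. post-difference of 0.03 in the monthly increase". The paired figure for the overall level change, also at 80% power, is an OR of 1.25, which the plan equates with a rise of 0.02 in probability. For a patient characteristic split 20:80, the slope claim is "80% power to detect an OR of 2.65 for the effect of patient characteristic on slope change", paired with a level-change OR of 1.73. The Aim 2 Sample Size/Power Analysis uses the same approach for a site-level strategy split 20:80. Its level-change OR is 1.80, and its slope figure is "an OR of 2.96 for the effect of an implementation strategy in slope change".

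The simulation took a pre-period level of 0.05 and a pre-period rise of 0.05 per month. These come from different outcomes: 0.05 is the level quoted for the complete bundle, and 0.05 per month is the rise quoted for element D. The correlations were 0.5 (AR(1)), 0.5 (within patient) and 0.6 (within hospital).

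The Aim 1 Data analysis section codes Month from -5 to 0 before implementation and 1 to 14 during it, with an Imp indicator and a Month by Imp product.

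Preliminary Data reports a segmented fit to monthly rates. For level change: "Complete bundle performance increased 2.0% (SE = 0.9" per cent, P = 0.057). For slope change: "each month was associated with 0.6% greater increase (SE = 0.2" per cent, P = 0.038). The pre-period trend was relatively flat.

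**The concern.** A slope change is measured per month over a 20-month series, while a level change is the gap between two fitted lines at the break. In this design the per-month slope change has the smaller standard error in most settings, so its detectable log-OR should usually be the smaller of the two. All three pairs show the reverse, by a similar factor. That suggests a systematic fault rather than a misprint.

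These are the plan's only power figures for trend effects, and the Aim 3 survey analysis uses the same model as Aim 2. As they stand, a reader cannot tell whether a null slope result, or a null level result, would be informative.

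**Working it through.** **1. Stated ratios.** Detectable log-OR = (1.960 + 0.842) × SE = 2.80 × SE, so at equal power and alpha the ratio of log-ORs is the ratio of SEs.

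| Pair (level/slope) | ln level | ln slope | slope/level |
|---|---|---|---|
| 1.25/1.52 | 0.223 | 0.419 | 1.88 |
| 1.73/2.65 | 0.548 | 0.975 | 1.78 |
| 1.80/2.96 | 0.588 | 1.085 | 1.85 |

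**2. Ratio from the month coding, flat trend.** The 6 pre-period months have mean -2.5 and sum of squares 17.5. The 14 implementation months have mean 7.5 and sum of squares 227.5. With equal information per month:

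- Slope-change variance: 1/17.5 + 1/227.5 = 0.0615, SE 0.248.
- Level-change variance at Month 0: 1/6 + 2.5²/17.5 + 1/14 + 7.5²/227.5 = 0.842, SE 0.918.
- Ratio: 0.27.

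With 5 patients per site-month before and 15 after (Aim 1, Procedures and Data Sources), the post-period terms are divided by 3. The SEs become 0.242 and 0.794, and the ratio 0.305. A common within-patient design effect cancels. AR(1) of 0.5 with equal months gives 0.32, and AR(1) of 0.9 gives 0.48. Measuring the level change at month 1 lowers the ratio, to 0.23 with equal months.

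**3. Ratio under the plan's steep pre-trend.** In a logistic model the weights n × p(1 - p) change with the trend. A rise of 0.05 per month around 0.05 corresponds to a logit slope of 0.747 (logit 0.10 minus logit 0.05) or 1.053 (0.05/(0.05 × 0.95)). The ratios are 0.67 and 0.91. Varying ICU intercepts, within-patient design effect, serial correlation and centring widened the range to 0.45 to 1.23. Nothing tried reached 1.8.

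**4. What one half implies for the other.**

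- If level OR 1.25 has 80% power, its SE is 0.223/2.80 = 0.080. At the highest ratio the slope SE is 1.23 × 0.080 = 0.098, and power for slope OR 1.52 is Φ(0.419/0.098 - 1.96), about 99%. The detectable slope OR would be 1.25^0.45 to 1.25^1.23, or 1.11 to 1.32. With a flat trend and AR(1) of 0 or 0.5 it would be about 1.05 to 1.08.
- If slope OR 1.52 is right, the level OR at the highest ratio is exp(0.419/1.23) = 1.41, and larger at any lower ratio.

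**5. Each half taken alone.** For 49,000 days the within-patient design effect is 1 (independent days) or 1 + 2.3 × 0.5 = 2.15 (3.3 days per patient).

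- Flat 0.05: level OR 1.38 to 1.60, slope OR 1.10 to 1.15.
- Steep pre-trend, without AR(1), with and without ICU intercepts: level OR 1.46 to 1.99, slope OR 1.27 to 1.70.

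The steep scenario brackets 1.52 but not 1.25. The flat scenario reaches neither.

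**6. Check against Preliminary Data.** Slope: 2.80 × 0.2 = 0.56 points per month, or 0.42 to 0.70 for an SE that rounds to 0.2 (0.15 to 0.25). The reported P = 0.038 on 16 df implies an SE of about 0.265, which gives 0.74. The stated 3 points per month is 3/0.74 = 4.0 to 3/0.42 = 7.1 times as large. If 3 points were the 80% limit, power for the observed 0.6 would be about 8% (0.6 × 2.80/3 = 0.56; Φ(0.56 - 1.96)). Level: 2.80 × 0.9 = 2.5 points, close to the stated 0.02.

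**7. Feasibility of the inputs.** Rising 0.05 per month to 0.05 at month 0 gives 0.05 - 5 × 0.05 = -0.20 at month -5. Adding 0.03 gives 0.08 per month, and 0.05 + 14 × 0.08 = 1.17. A monthly OR of 1.52 compounds to about 351 over 14 months. The OR-to-probability conversions depend on an unstated baseline: OR 1.25 is +0.012 from 0.05 and +0.022 from 0.10; OR 1.52 is +0.024 from 0.05; and 0.05 to 0.08 is OR 1.65.

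**The case against.** A reader might infer that the slope figures are the wrong half and should be withdrawn while the level figures stay. The documents do not support that. Under the plan's own steep pre-trend, a slope OR near 1.52 is attainable and the level OR of 1.25 looks too optimistic. With a flat 0.05 trend, even 49,000 independent days give a level OR of 1.38.

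A reader might also take the slope/level ratio as fixed at about a third by the month coding. That holds for a flat trend. In a logistic model with a steep trend the binomial weights raise it well above that.

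The factor of 4 to 7 might be read as applying to every slope figure. It belongs to 0.03 per month only. For OR 1.52 the factor depends on the baseline, and there is no preliminary standard error for 2.65 or 2.96, which are subgroup and site-strategy contrasts. Nor do the preliminary results contradict the power analysis outright. They come from a linear model on aggregated monthly rates with a flat pre-trend, and the slope SE does not match its own P-value: 0.6/0.2 on 16 df gives P of about 0.008.

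The strongest defence is that the random-effect variances are not stated, and random slopes could inflate the slope SE. To yield 1.52 from ICU slope variation alone, the SD would have to be 0.419 × √68/2.80 = 1.23 logits per month. Neither a value like that nor a time unit other than a month appears in the plan.

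Finally, the data are already collected, and the plan commits to point estimates and 95% confidence intervals whatever the power. That lowers the stakes but does not correct the figures.

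**Conclusion.** The concern holds in this form: the three level/slope pairs are mutually inconsistent. The stated log-OR ratios are 1.78 to 1.88, against about 0.2 to 0.5 with a flat or moderate trend and 0.45 to 1.23 under the steep pre-trend. At least one figure in each pair is wrong, or rests on inputs that the plan does not give. Separately, 0.03 per month is about 4 to 7 times the value implied by the preliminary complete-bundle slope SE, as a rough comparison. The assumed probabilities are infeasible on a linear scale.

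Which half is wrong remains open. If it is the slope half, the plan understates its power for trends; if it is the level half, it overstates its power for immediate changes. The conclusion assumes a monthly time unit, the stated month coding and enrolment, and no very large unstated random-slope variance. Severity is moderate.

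**What to change.** - Replace the probability-scale inputs with feasible logit-scale ones. State the baseline and the month it refers to, the pre-trend, the time unit of the slope OR, and the random-effect variances.
- Rerun the simulation for level and slope effects together.
- Restate all six ORs in the Aim 1 and Aim 2 power sections, each with a probability equivalent and the baseline it assumes.
- Check the overall level and slope figures against the standard errors in Preliminary Data and explain any remaining gap.
- Until then, mark all six figures as unverified rather than withdrawing the slope figures alone.

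The cost is a rerun of an existing simulation and edits to two paragraphs. No data collection or analysis model changes.
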